5.3. Exclusion Criteria

Subjects who meet any of the following criteria will be excluded from study participation:

1. Any relevant gastrointestinal (GI) surgery (excluding the gastric bypass or sleeve gastrectomy) per Investigator judgement
2. History of significant drug hypersensitivity or anaphylaxis
3. Participation in a weight loss program or clinical trial for weight loss within the 3 months prior to enrollment
4. Received any experimental drugs or devices or have participated in a clinical study within 30 days prior to enrollment
5. Diabetes treatment (unless metformin as outlined), or chronic oral steroids, or treatment with immune modulators, anti-obesity drugs, chronic opiate therapy, or antipsychotic medications
6. Currently receiving any drug-based therapy for weight management
7. Thyroid-stimulating hormone (TSH) level is outside of normal limit during the Screening Period
8. The presence of diseases with abnormal clinical manifestations that need to be excluded based on their possible contribution to weight loss or weight gain, including but not limited to nervous, cardiovascular, blood and lymphatic system, immune, renal, hepatic, gastrointestinal, respiratory, metabolic and skeletal diseases during the Screening Period
9. History of myocardial infarction, unstable angina, arterial revascularization, stroke, New York Heart Association Functional Class II-IV heart failure, or transient ischemic attack within 6 months prior to Visit 1
10. Any malignancy not considered cured (except focal, treated basal cell carcinoma and squamous cell carcinoma of the skin); a participant is considered cured if there has been no evidence of cancer recurrence in the previous 5 years
11. History of major depressive disorder or history of other severe psychiatric disorders (e.g., schizophrenia or bipolar disorder) within the last 2 years.
12. Donated ≥ 200 mL of blood (blood components) or had massive blood loss, received blood transfusion or blood products within 3 months prior to enrollment
13. Planned sperm/egg donation within 6 months post enrollment

14. Positive urine drug test (morphine, methamphetamine, ketamine, ecstasy, and cannabis) during the Screening Period
15. History of consuming more than 14 units of alcoholic beverages per week or of alcoholism or drug/chemical/substance abuse within past 2 years prior to enrollment (Note: one unit = 12 ounces of beer, 4 ounces of wine or 1 ounce of spirits)
16. Smoking any amount within 3 months prior to enrollment
17. Excessive consumption of tea, coffee, and/or caffeinated beverages (more than 8 cups, 250 mL for each cup) every day within 3 months prior to enrollment
18. Symptomatic viral, bacterial (including upper respiratory infection), or fungal (non-cutaneous) infection within 1 week prior to enrollment
19. History of human immunodeficiency virus antibody, hepatitis C antibody or hepatitis B virus surface antigen
20. A history of psychiatric and psychological condition that, in the judgment of the investigator, may interfere with the planned treatment and follow-up, affect subject compliance or place the subject at high risk from treatment-related complications
21. Poor venous access or inability to tolerate venipuncture
22. Any condition or active drug treatment that the investigator or primary physician believes may not be appropriate for participating in the study

5.4. Restrictions

5.4.1. Dietary and Fluid Restrictions

Caffeine

Subjects should not consume caffeine containing beverages exceeding 500 mg caffeine per day (5 cups of coffee) during the study.

Alcohol

Subjects should not consume more than 3 units (males) or 2 units (females) per day during the study (1 unit is equal to approximately ½ pint [284 mL] of beer, one small glass [125 mL] of wine, or one measure [25 mL] of spirits).

5.4.2. Lifestyle Considerations

Drugs of abuse

Subjects must refrain from use of recreational drugs including THC containing products for the duration of the study.

Nicotine

No smoking or use of other nicotine-containing products (snuff, chewing tobacco, cigars, pipes or nicotine-replacement products such as nicotine chewing gum and nicotine plasters) will be allowed during the study.

6. INVESTIGATIONAL MEDICINAL PRODUCT

6.1. Premedication

No pre-medication is required prior to administration of study medication. For subjects who experience Grade 2 acute allergic reactions and are able to continue on the treatment, premedication with an H1 antihistamine should be given.

6.2. Identity of the Investigational Medicinal Products

ARD-101 drug product is an encapsulated oral formulation of denatonium acetate monohydrate. The ARD-101 drug product will be supplied as white opaque body and white opaque cap hard gelatin capsules. The ARD-101 drug product contains 23.61 mg or 59.03 mg of denatonium acetate monohydrate (equivalent as 20 mg or 50 mg of denatonium base) together with povidone, sugar spheres, hypromellose, and talc as inactive ingredients.

6.3. Supply, Packaging, Labeling and Storage

Study drug will be supplied by Sponsor. The study medication will be packaged and labeled according to applicable local and regulatory requirements.

All supplies of study medication must be stored in accordance with the manufacturer's instructions. The ARD-101 will be stored at room temperature in a securely locked area, accessible to authorized persons only, until dispensation.

Further details will be provided in the Pharmacy Manual.

6.4. Drug Accountability, Dispensing and Destruction

The Principal Investigator or designee is responsible for maintaining accurate accountability records of the study drug throughout the clinical study. Products returned will be stored under the same conditions as products not yet dispensed.

All dispensing and accountability records will be available for Sponsor review. The Study Monitor will perform drug accountability at regular intervals.

Study medication will be dispensed for each subject according to the protocol and Pharmacy Manual.

After receiving Sponsor approval in writing, all unused or partially used study medication will be returned to the Sponsor or designated third party or for preparing the study medication for destruction via incineration.

6.5. Dose Modification

The dose level may not be reduced. If any \geq Grade 3 toxicities or any intolerable Grade 2 toxicity occurs, treatment should be discontinued permanently. Intolerable toxicity is defined as, in the opinion of Principal Investigator and Medical Monitor, any toxicity that poses a significant health risk to the subject. Treatment may continue on any Grade 1 toxic reactions or Grade 2 anorexia or Grade 2 weight loss. For any other Grade 2 toxicities, dosing may be interrupted for up to 3 days and may be resumed at the medical judgment of Investigator once the toxicity has resolved to Grade 0-1. A missed dose should not be made up. In the event of multiple toxicities, dosing management should be based on the worst toxicity observed. Subjects will be instructed to notify Investigators at the first occurrence of any adverse symptom.

6.6. Stopping Rules

At any time during the study, the subject must discontinue study drug treatment, if one of the following events occur:

- An increase of AST and/or ALT ($> 3x$ ULN) are observed in the presence of increased ($> 2x$ ULN) alkaline phosphatase and/or total bilirubin.
- A sustained AST or ALT increase, defined as three consecutive values of AST and/or ALT greater than $5x$ ULN within a period of 14 days.
- A treatment-related Grade 3 or greater adverse event (other than AST or ALT increase as described above) is noted by the Investigator.
- A relevant decrease of eGFR as per investigator

If any of the above stopping rules are met the following action(s) should be taken:

1. Stop dosing and convene a Safety Review Committee meeting;
2. Review AE for evidence of relationship to treatment;
3. May resume enrollment and continue the study if recommended by the Safety Review Committee.

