1.2. Schema

1.3. Schedule of Assessments, Time Points, and Window Allowance

Details on procedures and timing of assessments are presented in [Table 1](#).

Table 1 Schedule of Assessments

Period	Screening	Run-in Visit	Treatment Period (±3 days)			Follow Up/End of Study
			Study Days	-42 to -15	14 days prior to Day 1	
Informed Consent	X					
Inclusion/Exclusion Criteria	X					
Demographics	X					
Medical History	X					
Physical Examination ^a	X		X	X	X	X
Vital Signs	X		X	X	X	X
12-lead ECG	X		X		X	
Hematology	X		X ^b			X
Comprehensive Serum Chemistry	X		X ^b	X	X	X
Urinalysis	X		X ^b	X	X	X
Urine Toxicology	X					
Coagulation Parameters	X					
Pregnancy Test ^c	X		X ^b			X
TSH	X					
Weight/BMI	X	X	X	X	X	X
Height	X					
Fasting Glucose		X				X
HbA1c	X				X	
Waist Circumference			X	X	X	X
Fasting Blood Lipids		X			X	
Fasting Circulating Hormones ^d			X			
Bioimpedance			X	X	X	

Period	Screening	Run-in Visit	Treatment Period (±3 days)			Follow Up/End of Study
			Study Days	-42 to -15	14 days prior to Day 1	
MRI PDFF + Full Body Composition Scan		X			X	
Mixed Meal Tolerance Test (MMTT)		X			X	
Study Drug Dispensation			X ^e			
Concomitant Medication	X		X	X	X	
Indirect Calorimetry		X			X	
Adverse Event Monitoring	X		X	X	X	X
CGM Placement		X		X		
CGM Removal and Download			X		X	X
Fecal Sample Collection ^f		X			X	
Phenotypic Bitter Taste Test ^g		X				
Control of Eating Questionnaire (CoEQ)	X		X	X	X	X

- a. Complete physical examination at screening, and brief physical examination for all follow-up visits
- b. This procedure is not needed if performed within 3 days
- c. For women of child-bearing potential only
- d. GLP-1 (total and active), CCK, PYY, amylin, GIP (total and active), ghrelin, leptin, and adiponectin in all subjects at 3 time points (before the first dosing and 1h as well as 2h after the first dosing)
- e. A single oral dose of oral ARD-101 will be administered to subjects in the morning of day 1
- f. Fecal sample to be collected during run-in visit and on day 28. Optional for subjects
- g. Phenotypic bitter taste test is optional for subjects

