8.2.2. Clinical Laboratory Assessments

Samples for clinical laboratory assessments will be collected at the time points detailed in the Schedule of Assessments (Table 1). Samples will be collected in appropriate tubes and handled according to standard procedures of the applicable laboratory.

Any value outside the normal range will be flagged for the attention of the Principal Investigator or designee at the site. The Principal Investigator or designee will indicate whether the value is of clinical significance. Additional testing during the study may be done if medically indicated. If a clinically significant abnormality is found in the samples taken after dosing, during the study, and/or at the EOS Visit, it should be recorded as an AE and the subject will be followed until the test(s) has (have) normalized or stabilized, at the discretion of the Principal Investigator.

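### The chemistry draws in Table 1 cannot by themselves meet the sustained AST/ALT stopping rule in 6.6 while dosing continues, and 6.5 and 6.6 disagree on what an isolated rise requires

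*Combined protocol and SAP*

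**What the plan says.** Section 6.6 opens with a mandatory instruction: "the subject must discontinue study drug treatment, if one of the following events occur". Three of its four bullets bear on the liver.

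- **Bullet 1** covers AST and/or ALT above 3x ULN, but only where these "are observed in the presence of increased" (above 2x ULN) alkaline phosphatase and/or total bilirubin.
- **Bullet 2** is the rule for a transaminase rise on its own: "A sustained AST or ALT increase, defined as three consecutive values of AST and/or ALT greater than" 5x ULN, all "within a period of 14 days".
- **Bullet 3** reads: "A treatment-related Grade 3 or greater adverse event (other than AST or ALT increase as described above) is noted by the Investigator".

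Meeting any bullet also means convening a Safety Review Committee.

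Section 6.5, immediately before, ends treatment permanently for any toxicity of Grade 3 or above and for intolerable Grade 2 toxicity. It makes no exception for AST/ALT and does not mention the committee.

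In Table 1 the row "Comprehensive Serum Chemistry" is marked at Screening, at the three treatment visits and at Follow-up/End of Study. It is blank at Run-in. The first treatment mark carries footnote b: "This procedure is not needed if performed within 3 days".

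On repeat testing, 8.2.2 says: "Additional testing during the study may be done if medically indicated". It adds that a clinically significant post-dose abnormality is recorded as an AE and followed until the test normalizes or stabilizes, at the Principal Investigator's discretion. Section 8.2.1.5 likewise requires AEs and abnormal laboratory values to be monitored to resolution or stabilization.

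**The concern.** Bullet 2 is written as a compulsory stop, yet it needs more values, closer together, than the visit schedule supplies. If the middle-visit chemistry shows an isolated AST or ALT above 5x ULN, the site holds one value, and the next scheduled one comes at about the end of dosing. Whether bullet 2 is ever tested during treatment then depends on when the investigator chooses to redraw.

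The same site must also decide which section applies. Under 6.5 a single value may be enough, if it grades as 3. Under 6.6 three may be needed. Only the 6.6 route brings in the Safety Review Committee. Two sites, or one site on two occasions, could follow the protocol and act differently.

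This matters more because the longest human dosing the protocol reports is 14 days (2.4 and 2.4.1.2), while this trial doses for 28.

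**Working it through.** The plan gives no figure to reproduce. The check is a count of draws and a comparison of spans with the window.

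**Inputs**

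- Values needed: 3 consecutive, within 14 days (6.6, bullet 2).
- Scheduled chemistry: Screening, three treatment visits, End of Study (Table 1).
- First treatment visit: Day 1. The first-dose footnotes sit in this column, and 9.7 treats pre-dose Day 1 measurements as baseline.
- Last treatment visit: Day 28. The mixed-meal test is marked there and 3.3 places it on day 28. With the ±3-day window, this is Days 25 to 31.
- Middle visit: its day label is not legible in the text available. Day 14 is an assumption, supported by the 14-day glucose sensor (8.2.10) being placed at this visit and removed at the last treatment visit. With the window, this is Days 11 to 17.
- End of Study: within 14 days after the last dose (4.1). With the last dose assumed on Day 28, this is Days 29 to 42.
- Entry limit for AST/ALT: 1.5x the upper norm (5.2, criterion 9).

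**Step 1. Post-dose draws during treatment.** Middle visit + last visit = 2, against 3 required. The rule is one value short.

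**Step 2. Add the pre-dose Day 1 draw.** Span = last visit − first visit.

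- Day 1 fixed, last visit at its earliest: 25 − 1 = 24 days.
- Day 1 also moved by +3: 25 − 4 = 21 days.

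Both exceed 14. An earlier draw used under footnote b only lengthens the span. Given the entry limit, a Day 1 value above 5x ULN should not occur in any case. Steps 1 and 2 do not depend on the day of the middle visit.

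**Step 3. Use End of Study as the third value.** Span = End of Study − middle visit.

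- Nominal: 42 − 14 = 28 days.
- End of Study on Day 42, middle visit at its latest: 42 − 17 = 25 days.
- All permitted whole-day combinations with End of Study after the last treatment visit: 7 × (4×14 + 13 + 12 + 11) = 7 × 92 = 644.
- Combinations with a span of 14 days or less need the (middle, End of Study) days to be (15, 29), (16, 29), (16, 30), (17, 29), (17, 30) or (17, 31). The count is 4 + 4 + 5 + 4 + 5 + 6 = 28 of 644.

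This is a count of calendar possibilities, not a probability. In every one of the 28 the third value comes after the last dose, so nothing is left to stop.

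**Step 4. Set 6.5 beside 6.6 for an isolated rise.**

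- *6.5:* one finding suffices if it is Grade 3 or above. But 8.2.1.2 only names a toxicity scale, 8.2.1.3.1 defines grades by symptoms and daily activities, and no AST/ALT cut-offs are printed. The documents do not show which grade a value above 5x ULN receives.
- *6.6, bullet 3, broad reading:* every AST/ALT increase is excepted, leaving bullet 2 as the only 6.6 rule for an isolated rise.
- *6.6, bullet 3, narrow reading:* only increases already meeting bullets 1 or 2 are excepted, so a treatment-related Grade 3 isolated rise triggers bullet 3 on one value.

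The broad reading conflicts with 6.5. The narrow reading agrees with 6.5 on stopping, but bullet 2 then adds something only for rises that are not graded 3 or are not judged treatment-related. Under either reading, the committee meeting follows from 6.6 and not from 6.5.

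**The case against.** The best defence is that bullet 2 was never meant to run on scheduled visits. It does not restrict itself to scheduled values. Sections 8.2.2 and 8.2.1.5 expect a clinically significant abnormality to be followed until it settles, which for a laboratory value means repeat draws. In the meantime 6.5 can stop treatment for Grade 3 toxicity without waiting for three values, and 4.1 lets the principal investigator stop treatment at discretion. None of the treatment-related events in Table 7 of the earlier study is hepatic.

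Most of this stands, and it rules out three stronger conclusions that a reader might draw.

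- *No repeat test is called for after a high value.* The follow-up wording in 8.2.2 and 8.2.1.5 contradicts this. What is missing is a trigger level and an interval.
- *A report that no subject met the hepatic stopping rules would be empty by design.* It would not. Bullet 1 is a hepatic rule that one scheduled draw can trigger, and unscheduled values count towards bullet 2.
- *An isolated rise has no stopping rule other than bullet 2.* Section 6.5 may apply, and so may bullet 3 on its narrow reading.

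The defence does not remove the gap itself. A compulsory stop still rests on draws whose need and timing are left to discretion, with nothing that makes them fall inside the rule's own 14 days. And relying on 6.5 as the backstop exposes its disagreement with 6.6 rather than resolving it.

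**Conclusion.** The inconsistency is real, with limited consequences. On scheduled tests alone, bullet 2 of 6.6 cannot be met during treatment: two post-dose draws against three required, or a span of at least 21 to 24 days against 14 if Day 1 is counted. This holds whatever the day of the middle visit. Only the 28-of-644 exception depends on the Day 14 assumption and on a last dose on Day 28, and it arises only after dosing has ended.

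The rule is workable through unscheduled follow-up, so it is not inoperable and subjects are not without protection. The defect is that a mandatory safety stop depends on discretionary draws with no timing tied to its window, and that 6.5 and 6.6 do not give one answer for an isolated AST/ALT rise. The documents do not settle which section governs, because bullet 3's exception is ambiguous and the laboratory grade limits are not printed.

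**What to change.** Reconcile 6.5, 6.6, 8.2.2 and Table 1 on two points.

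1. **Sampling.** Make the sampling that the protocol requires, scheduled or follow-up, able to deliver the values bullet 2 needs within bullet 2's own window. State this where the site will look for it, in 8.2.2 or as a footnote to Table 1.
2. **One rule.** Have 6.5 and 6.6 say the same thing about an isolated AST/ALT rise. State how far the exception in bullet 3 reaches, which grading limits apply to AST/ALT, and whether the Safety Review Committee is convened when treatment stops under 6.5.

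The threshold, the number of values and the dosing decision are clinical matters for the sponsor, and none is proposed here. The cost is protocol wording and, depending on how the passages are reconciled, a few unscheduled chemistry draws in subjects with a high value.

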6.7. Subject Identification

6.7.1. Screening Numbers

All screened subjects are assigned a unique screening number. The screening numbers are numbers that identify subjects from time of screening until time of enrollment.

6.7.2. Enrollment Numbers

Eligible subjects will be assigned an enrollment number. The enrollment number will include 6-digit site number and subject numbers starting with 201 as below.

- Subject 100-201

Once an enrollment number has been allocated to one subject, it may not be assigned to another subject.

6.8. Compliance

Dosing will be performed by trained, qualified personnel designated by the Principal Investigator.

6.9. Special Precautions and Management of AEs

6.9.1. Eating disorders

ARD-101 may decrease appetite and subsequently change a subject's eating behavior by delaying gastric emptying and inducing the glucagon-like peptide-1 and cholecystokinin secretion into the circulation that targets the central nervous system (CNS) to cause satiety/hunger sensation. Subjects who develop any eating disorders during study treatment should be permanently discontinued from study drug.

6.9.2. Allergic reactions

One case of allergic reaction has been reported in a female subject receiving denatonium benzoate, a compound in the same class as ARD-101 ([Deloose E et al. 2017](#)). Drug allergic reactions can be either acute or delayed. The acute allergic reactions that usually occur within 1 h after drug exposure are typically IgE mediated while those that usually occur 2 to 6 h after drug exposure have more complicated pathophysiological mechanisms. Subjects with a localized Grade 2 acute allergic reaction might continue on the treatment with premedication of H1 antihistamine. Subjects with recurrent Grade 2 acute allergic reactions with premedication, Grade 2 delayed allergic reactions, or Grade 3 to 4 acute allergic reactions should permanently discontinue the study drug.

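### Sections 6.5 and 6.9.2 conflict on some Grade 2 allergic reactions: a subject whom 6.9.2 stops permanently could be re-dosed under 6.5, and the protocol does not say which section prevails.

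*Combined protocol and SAP*

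**What the plan says.** Three sections of the protocol bear on a Grade 2 allergic reaction.

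- **Section 6.9.2 (Allergic reactions)** directs a permanent stop for three groups: Grade 2 acute reactions that recur with premedication, and then "Grade 2 delayed allergic reactions, or Grade 3 to 4 acute allergic reactions should permanently discontinue the study drug". For a milder presentation it says: "Subjects with a localized Grade 2 acute allergic reaction might continue on the treatment with premedication of H1 antihistamine".
- **Section 6.5 (Dose Modification)** sorts toxicities by grade. A permanent stop applies at Grade 3 or above, or when "any intolerable Grade 2 toxicity occurs, treatment should be discontinued permanently". Intolerable means, in the opinion of the Principal Investigator and Medical Monitor, "any toxicity that poses a significant health risk to the subject". It also says: "Treatment may continue on any Grade 1 toxic reactions or Grade 2 anorexia or Grade 2 weight loss". Everything else at Grade 2 falls under: "For any other Grade 2 toxicities, dosing may be interrupted for up to 3 days and may be resumed at the medical judgment of Investigator", on condition that the toxicity has come down to Grade 0–1.
- **Section 6.1 (Premedication)** says: "For subjects who experience Grade 2 acute allergic reactions and are able to continue on the treatment, premedication with an H1 antihistamine should be given".

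None of the three sections refers to another, and the protocol has no rule of precedence among them.

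**The concern.** Section 6.5 is worded as a complete scheme for Grade 2 toxicity, with only two named exceptions, and allergy is not one of them. Section 6.9.2 removes the investigator's discretion for two kinds of Grade 2 allergic reaction. Staff working from 6.5 could resume dosing in a subject whom staff working from 6.9.2 would stop for good. What is at stake is re-exposure of an outpatient after an allergic reaction to a drug that has already been associated with urticaria. A lesser consequence is that some discontinuations, and so some subjects' Day 28 weight, could depend on which section was read.

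**Working it through.** The conflict itself involves no arithmetic. The check reads each type of Grade 2 allergic reaction through the three sections.

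| Grade 2 reaction | Section 6.9.2 | Section 6.5 | Section 6.1 | Result |
|---|---|---|---|---|
| Delayed | Permanent stop | May interrupt and resume unless judged intolerable | Silent | Conflict between 6.5 and 6.9.2 |
| Acute, recurring on premedication | Permanent stop | May interrupt and resume unless judged intolerable | No limit on recurrence | Conflict between 6.5 and 6.9.2 |
| Acute, first, localized | May continue with antihistamine | May interrupt and resume; premedication not mentioned | Premedicate if able to continue | Different emphasis, but all three can be followed |
| Acute, first, not localized | No instruction | May interrupt and resume unless judged intolerable | Premedicate if able to continue | Gap in 6.9.2; scope differs from 6.1 |

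Next, a search for a tie-breaker elsewhere. The general adverse-event trigger in Section 6.6 (Stopping Rules) starts at treatment-related Grade 3, so it does not reach these cases. The intolerable clause in 6.5 depends on an opinion in each case, whereas 6.9.2 asks for no such opinion in the first two rows. Section 10.7 requires the protocol to be followed exactly, which does not help when two sections differ.

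The acute/delayed split also matters, because 6.9.2 makes the action depend on it. The section describes onset as usually within 1 h for one kind of reaction and usually 2 to 6 h for the other. These are typical timings rather than class limits, and it is not stated how to class an onset between 1 and 2 h, or after 6 h.

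Last, relevance. Inputs are from Section 2.4.3 and Tables 6 and 7 (14-day multiple-dose part).

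- Subjects on ARD-101: 4 + 5 + 4 = 13.
- Treatment-related urticaria: 1 at 100 mg BID and 1 at 240 mg BID, so 2/13 = 15.4%. The exact (Clopper-Pearson) 95% interval is 1.9% to 45.4%.
- Section 2.4.3 gives the 100 mg case as Grade 1. The grade of the 240 mg case is not stated. Table 6 has one treatment-related Grade 2 event at 240 mg BID, and Table 7 lists six preferred terms at that dose, urticaria among them, without grades. So at most 1 of the 13 subjects had Grade 2 urticaria, and possibly none did.
- Onset times are not given, and no reaction is described as delayed.

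**The case against.** The strongest reply is that 6.5 only permits. Dosing may be interrupted and may be resumed, so an investigator who stops a subject under 6.9.2 breaches nothing in 6.5. Section 6.9.2 is also the more specific text and sits under special precautions, and a serious enough reaction could be called intolerable. This stands in part: the two sections do not give opposite orders, and the right word is that a subject could be re-dosed, not would be. It does not remove the problem. An investigator who resumes dosing under 6.5 is also within the text, and the protocol nowhere says that the specific section overrides the general one.

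A reader might infer more than the documents support on four points.

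- **That 6.1 is a third contradictory order.** It applies only to subjects already able to continue and only to acute reactions. It does not direct re-exposure of anyone whom 6.9.2 stops. It differs in scope, because it lacks the localized limit.
- **That the onset times leave a forbidden hour around peak exposure.** Median tmax in Table 5 is 1.08 to 1.75 h, but the onset bands are hedged with usually, and no text links allergic onset to plasma peak. The timings are an ambiguity, not a contradiction.
- **That 5 to 7 of 30 subjects would meet the conflict.** Those counts come from 30 × 2/13 = 4.6 and 30 × 2/9 = 6.7 (the 9 being subjects at 100 or 240 mg BID). They count urticaria of any grade and any onset, which is not the event in conflict.
- **That the primary endpoint is materially affected.** Section 4.5 asks for the usual data at premature discontinuation and Section 7.1 allows replacement. No effect on percent weight change can be quantified.

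**Conclusion.** The conflict between 6.5 and 6.9.2 is real, in operative text, and needs correcting. It covers two situations: Grade 2 delayed reactions, and Grade 2 acute reactions that recur on premedication. The scope mismatch with 6.1, the missing instruction for a first non-localized Grade 2 acute reaction, and the loose acute/delayed distinction are secondary.

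The frequency of the conflict in this trial cannot be estimated from the documents. The 2 of 13 figure shows that hypersensitivity is relevant. It comes from healthy volunteers dosed for 14 days, whereas this trial gives 200 mg BID for 28 days to subjects after bariatric surgery. The case for acting rests on subject safety, not on a projected count or on bias in the weight endpoint. The conclusion assumes only that the three sections are read as written, with no precedence rule in another document such as a site manual.

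**What to change.** The sponsor's clinical team, with the Medical Monitor, should reconcile Sections 6.1, 6.5 and 6.9.2 by amendment:

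- state which section governs allergic reactions, and add cross-references among the three;
- use the same scope wording in 6.1 and 6.9.2, so that localized and non-localized Grade 2 acute reactions are each covered;
- word the acute/delayed distinction so that a reaction with any onset time can be classed.

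Which action applies to each kind of reaction is the sponsor's clinical decision, and no view on it is offered here. The cost is a change of wording in three sections and the usual ethics approval of an amendment. No procedures, visits or subjects are added.
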